
D2. Study Population & Eligibility Criteria

The study will be based at the ambulatory obstetrical practices of Baystate Medical Center, a large tertiary care facility in Western Massachusetts that serves a socioeconomically diverse population; 4,300 infants are delivered annually, 57% are Hispanic (predominantly from Puerto Rico with ~58% having income <\$15,000 per year). Eligible women will be Hispanic, overweight or obese (BMI >25 kg/m²), and 16-45 years of age. We will exclude women with 1) prepregnancy BMI <25 kg/m², 2) history of type 2 diabetes, heart disease, or chronic renal disease, 2) contraindications to participation in moderate physical activity or to a low-fat/high-fiber diet (e.g., Crohn's disease, ulcerative colitis), 3) inability to read English or Spanish at a 6th grade level, 4) <16 or >45 yrs of age, 5) >20 wks gestation, 6) current medications which adversely influence glucose tolerance, 7) not planning to continue to term or deliver at the study site, or 8) pregnant with twins or triplets. Women who have a very early preterm birth (<34 wks), a miscarriage, or a still birth after enrollment or a stillbirth will be excluded. Women who become pregnant again in the year following delivery will be censored at the time of their positive pregnancy test.

D3. Recruitment, Baseline Assessment, and Sample Size

Bilingual (Spanish and English) and bicultural health educators will recruit women at the first prenatal care visit (~10 wks gestation). Women will be informed of the aims/procedures of the project, sign an informed

consent, and complete a screening form to determine eligibility. The baseline assessment will be collected via standardized questionnaire and the pregnancy blood sample will be taken (see Figure 1). Expectations for the study and a contacts schedule (face-to-face meeting, mailings, booster telephone calls) will be reviewed. Each assessment and interview completed is associated with a gift card for a total of up to \$360, to be handed out after completing the study component.

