Specific Aim #4: Evaluate the impact of a Lifestyle Intervention on the outcomes of offspring. We will evaluate the impact of intervention arm on the offspring outcomes using the methods described for Aim #1-3. We will also examine GWG and prenatal glycemic factors as predictors of glycemia and weight gain in early infancy and childhood. Important covariates are listed in the covariate section. In models focused on offspring weight gain as the outcome, we will additionally adjust for fetal growth (i.e., BW/GA z score).

Specific Aim #5: Evaluate the cost-effectiveness of the Lifestyle Intervention. We will use procedures developed in our prior studies examining the cost-effectiveness of our interventions.¹⁷¹⁻¹⁷³ We will calculate the ratio of average dollars spent per average incremental improvement in outcome (i.e., GWG, postpartum weight retention, and biomarkers of insulin resistance and CVD risk). Incremental improvement will be defined as the mean change score from baseline for each group, adjusted for baseline values of the outcome measure and other participant characteristics.

Accounting for Missing Data: Although every effort is made to avoid missing data, we plan to use propensity score techniques¹⁷⁴⁻¹⁷⁶ to evaluate the potential sensitivity of results to missing at random assumptions. Multiple comparisons will be addressed by carefully considering the biologic rationale of observed associations.

D.17. Power

To achieve power to detect clinically significant differences requires 300 participants (150 in each intervention arm) at the time of delivery. Based on observed rates in our 2 trials (R01DK074876 and

ASPH/CDC S3948), we conservatively expect 10% of women to leave the New England area, deliver elsewhere, or withdraw during pregnancy, and therefore will recruit 333 women over the 24 mos recruitment period. For offspring outcomes, we calculate that 4% will be excluded for very early preterm birth (<34 wks), miscarriage, or stillbirth resulting in 288 children at delivery. Over the following 1 yr, we conservatively project that an additional 8% of women will be lost to follow-up due to withdrawal or movement out of the New England area. Women who become pregnant again will be censored. Therefore, we expect 264 women and children at 1 yr postpartum.

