We calculated the smallest mean difference in change from baseline in the Lifestyle Intervention vs. the Health & Wellness Control arm which we could detect at 80% power using standard deviations based on our prior studies and the literature^{47, 177-180} using 2-sided tests with a significance level of alpha=5% (NCSS PASS 2008 software). For multiple regression models, we assumed that covariates accounted for 20% of the variation. Tables 3 and 4 show we have excellent power to detect even ‘small to medium’ mean differences, as defined by Cohen,¹⁸¹ ranging from ~0.30 to 0.35 SDs for a range of representative outcome measures. For example, we have 80% power to detect as small as a 2.4% difference (Table 3) in percent change in HbA1c between treatment arms. A comparable trial among Hispanics observed a 7.1% difference in percent change in HbA1c between treatment arms¹⁸² demonstrating that detecting this difference is well within the capability of the lifestyle intervention. For the categorical outcome of Compliance with IOM GWG guidelines, given our observation that 51% of overweight/obese Hispanic women exceeded guidelines in the study population, we have 80% power to detect a 30% reduction in risk or larger for exceeding IOM guidelines.

Table 3. Power Calculations Corresponding to Aim #1-3.	Projected sample size for analysis	SD for Change from Baseline	Smallest detectable mean difference in change from baseline between arms
Aim #1: GWG & Postpartum Weight Loss			
GWG (kg)	300	7.00	2.3
Postpartum weight loss	264	6.00	2.1
Physical activity (MET-hrs/wk>mod intensity)	300	2.89	0.9
Physical activity (minutes>mod intensity)	300	38.05	12.3
Total Caloric Intake (kcal/day)	300	64.90	22.4
Aim #2: Biomarkers of Insulin Resistance			
Glucose (mg/dl)	300	13.27	4.3
Insulin (pmol/l)	300	14.20	4.6
HbA _{1c}	300	0.26	0.1
HbA _{1c} (percent change)	300	7.4%	2.4%
Adiponectin (μg/ml)	300	3.40	1.1
Leptin (ng/ml)	300	5.50	1.8
HOMA	300	1.00	0.3
Aim #3: Postpartum Biomarkers of CVD Risk			
Total cholesterol (mg/dL)	264	38.38	13.3
Triglycerides (mg/dL)	264	83.06	28.7
HDL-cholesterol (mg/dL)	264	7.59	2.6
LDL-cholesterol (mg/dL)	264	33.83	11.7
Systolic blood pressure (mm Hg)	264	12.23	4.2
Diastolic blood pressure (mm Hg)	264	7.64	2.6
CRP (mg/dl)	264	4.50	1.5

Table 4. Power Calculations Corresponding to Aim #4.	Projected sample size for analysis	SD	Smallest detectable mean difference between arms
Aim #4: Offspring Outcomes at Delivery			
Cord glucose (mg/dl)	288	14	4.6

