At the time of recruitment (~10 weeks gestation), a blood sample to evaluate serum biomarkers associated with insulin resistance and other cardiovascular risk factors will be collected (termed "blood draw"). A total 700 microliters (uL) of serum will be collected which is equivalent to 1.5 milliliters (mL) or less than a teaspoon of whole blood. Physical activity, diet, and other covariates will also be assessed at recruitment. Subsequent assessments will be conducted at ~24-28 weeks gestation, after 32 weeks gestation, 6-weeks postpartum, ~6.5-months, and ~13-months postpartum. A urine pregnancy test will also be performed at the postpartum assessments. Women who are identified as having a positive pregnancy test will be removed from the study at the time of their positive pregnancy test and referred to their obstetric care provider. Measurements of compliance with exercise and diet will include activity monitors (worn for a 4-day period within each of these assessment time points), tracking the number of intervention sessions attended, number of booster calls participated in, number of assessments (e.g., questionnaires, blood samples) completed, as well as an assessment of degree of participation in physical activity and healthy dietary behaviors. No participants will be excluded from the study based on noncompliance. Assessments to measure other important covariates will also be collected at these assessment time points. Subjects will be under no obligation to complete the assessments, activity monitoring, or blood collections. Pregnancy and postpartum medical and laboratory records will be reviewed for obstetric and medical history, clinical characteristics of the index pregnancy, and laboratory results. All data will be used specifically for research purposes.

Potential Risks:

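### The 264 women expected at 1 year postpartum leave no room for the repeat-pregnancy censoring that the plan imposes

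*Combined protocol and SAP*

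**What the plan says.** D.17 (Power) starts from a design that "requires 300 participants (150 in each intervention arm) at the time of delivery". It then states that "4% will be excluded for very early preterm birth (<34 wks), miscarriage, or stillbirth resulting in 288 children at delivery", and that over the following year "an additional 8% of women will be lost to follow-up due to withdrawal or movement out of the New England area". The chain ends with "Women who become pregnant again will be censored. Therefore, we expect 264 women and children at 1 yr postpartum". D3 gives the same sequence and the same end figure.

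The censoring rule itself is in D2: "Women who become pregnant again in the year following delivery will be censored at the time of their positive pregnancy test". Section E.1 (Sources of Materials) goes further and says that such women "will be removed from the study at the time of their positive pregnancy test". D.12.4 and E.1 schedule a urine pregnancy test at the postpartum assessments, and E.1 places the last of these at about 13 months.

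Table 3 uses N=264 for postpartum weight loss and for all seven Aim 3 rows. The 1-year offspring rows of Table 4 use the same number.

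**The concern.** The closing sentences of the chain read as though 264 already allowed for repeat pregnancy. But the 8% is tied to other named causes, and the censoring sentence carries no percentage. A woman removed after a positive test has no 1-year weight, lipid, blood pressure or CRP value. The plan tests for this event and has a rule for it, yet the sample-size chain gives it a rate of zero without saying so.

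At stake are the stated 1-year maternal N and the power claim for postpartum weight loss and Aim 3 at that time point.

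**Working it through.** **Inputs.** From D.17: 300 at delivery in two equal arms; 4% exclusion; 8% loss; two-sided alpha of 5%; 80% power; covariates assumed to explain 20% of the variation in multiple regression models. From Table 3: postpartum weight loss N=264, SD 6.00, detectable difference 2.1 (taken as kg); total cholesterol N=264, SD 38.38, detectable difference 13.3 mg/dL. The repeat-pregnancy rate r is not given, so it is assumed below.

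**Step 1: reproduce 264.**
- Recruitment: 333 x 0.90 = 299.7, taken as 300.
- After delivery exclusions: 300 x 0.96 = 288.
- After loss to follow-up: 288 x 0.92 = 264.96. Adding the two losses instead gives 300 x (1 - 0.04 - 0.08) = 264.0.

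Either way, the two stated losses account for the figure, and at most one woman is left for repeat-pregnancy censoring.

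**Step 2: reproduce Table 3.** With n per arm, the normal approximation to the detectable difference is (1.960 + 0.842) x SD x sqrt(2/n). At n = 132 this gives 2.07 kg and 13.24 mg/dL. The two-sample t-test (noncentral t) gives 2.08 kg and 13.28 mg/dL, matching the printed 2.1 and 13.3. Power at the printed differences is 80.9% and 80.1%.

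With the 20% covariate assumption the SD would be multiplied by sqrt(0.80), and the detectable differences would be 1.86 kg and 11.9 mg/dL. The table therefore uses the full 264 with no covariate reduction, and has almost no margin.

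**Step 3: allow for repeat pregnancy.** Set N = 264 x (1 - r) and repeat the unadjusted t-test.

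| Assumed r | N | Detectable weight difference (kg) | Power at 2.1 kg | Power at 13.3 mg/dL |
|---|---|---|---|---|
| 0 | 264 | 2.08 | 80.9% | 80.1% |
| 5% | 250.8 | 2.13 | 78.8% | 78.0% |
| 10% | 237.6 | 2.19 | 76.6% | 75.8% |
| 15% | 224.4 | 2.25 | 74.2% | 73.4% |

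Unadjusted power at 2.1 kg drops below 80% once r passes about 2.2%.

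**Step 4: the same with the 20% covariate reduction.** Power at 13.3 mg/dL is about 88% at r = 0, 86% at 5%, 84% at 10%, 82% at 15% and 80% at 20%.

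**The case against.** The strongest reply is that the plan has slack it does not display. D.17 assumes that covariates explain 20% of the variation in regression models, and D.16 describes the primary model as corresponding to an analysis of covariance. If that 20% were realised, Step 4 shows power holding at about 80% or above up to roughly 20% censoring. This stands as a limit on the consequence. It does not rescue the printed figures, which take no such credit, and it is uncertain whether 20% would be gained on top of an SD that is already for change from baseline.

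Second, censoring is not retrospective exclusion. The primary analysis in D.16 is a mixed model with a random effect for each subject, so values from before the positive test remain in use. Blood is drawn at 6 weeks and 6 months as well as 1 year (D.12.1), weight change is defined at both 6 and 12 months (D.12.3), and the Table 3 rows are not labelled as 1-year rows. This also stands, and it narrows the point to 1-year maternal contrasts. It does not supply the missing 1-year measurements, and D.17 describes 264 as the number at 1 year.

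Third, the closing inference to 264 may simply sum up the whole chain, with the censoring sentence as a handling rule. That is a fair reading of loose drafting. On that reading too, the loss has no number.

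Fourth, the rates in Step 3 have no basis in the documents. That is correct: only the direction is established. At 5% the detectable weight difference still rounds to the printed 2.1.

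**Conclusion.** The stated 1-year maternal N omits a loss that the plan itself imposes. For any nonzero repeat-pregnancy rate, 264 is too high for mothers at 1 year. So is the unadjusted 80% power behind the postpartum weight and Aim 3 rows of Table 3, when these are read as 1-year contrasts. The size cannot be found from the documents. At assumed rates of 5% to 15% it costs about 2 to 7 percentage points of power, and the detectable weight difference rises by up to 0.17 kg (2.08 to 2.25).

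Three stronger inferences are tempting, and the documents do not support them:
- **That the trial will fall short of 80% power.** No rate is given, and the assumed covariate contribution could absorb the loss.
- **That censored women drop out of the postpartum analysis altogether.** Their 6-week and 6-month values from before censoring stay in the mixed model.
- **That the children's 264 in Table 4 is wrong.** The documents do not say whether a child leaves follow-up when the mother is censored.

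Gestational weight gain and the other N=300 rows are not affected.

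**What to change.** - Add an assumed repeat-pregnancy percentage, with its source, to the attrition chain in D3 and D.17.
- Restate the 1-year maternal N, and the Table 3 detectable differences for postpartum weight loss and Aim 3 at that N. State whether the 20% covariate reduction is applied.
- Give the children's 1-year N separately, and state whether a child stays in follow-up after the mother is censored.

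This changes stated figures only. It needs no extra enrolment and no change to the design; the cost is slightly less favourable numbers in Table 3.

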Fasting Glucose (FG) will be measured enzymatically on the Roche P Modular system using Roche Diagnostics reagents (Indianapolis, IN).¹⁵⁵ Glucose at the concentrations of 90 and 312 mg/dL are determined in [name] laboratory with a day-to-day variability of 1.7 and 1.6%, respectively. Fasting Insulin (FI) will be measured by an electrochemiluminescence immunoassay on the Roche E Modular system. The lowest detection limit of this assay is 0.2 uU/mL and the day-to-day imprecision values at concentrations of 6.36, 20.9 and 747 uU/mL are 2.6, 2.8 and 2.5%, respectively. HOMA: Homeostasis model assessment will be calculated as [(FI x FG)/22.5] on a scale of 1-8. The Hemoglobin A1c (HbA1c) determination on the Roche P Modular system will be based on turbidimetric immunoinhibition using packed red cells. The day-to-day variability at values of 5.5 and 9.1 are 1.9 and 3.0%, respectively. Total Adiponectin (Multimeric) will be measured using an ELISA method from ALPCO Diagnostics Inc. (Salem, NH); day-to-day variabilities at concentrations of 9130 and 3930 are 9.8, 10.2%, respectively. Leptin will be measured by an ultra-sensitive ELISA assay, an enzymatically amplified “two-step” sandwich-type immunoassay (R&D Systems, Minneapolis, MN); day-to-day variability at concentrations of 65.7, 146 and 581 pg/mL are 5.4, 4.2 and 3.5%, respectively. Lipoprotein Profile: will be simultaneously performed on the Roche P Modular system. [name] laboratory is certified by the CDC/NHLBI Lipid Standardization Program.¹⁵⁶ Total Cholesterol will be measured enzymatically.¹⁵⁷ At cholesterol concentrations of 132.8 and 280.4 mg/dL, the day-to-day reproducibility are 1.7% (SD=2.4 mg/dL) and 1.6%, respectively. Triglycerides will be measured enzymatically with correction for endogenous glycerol.¹⁵⁸ Triglycerides at concentrations of 84.0 and 201.8 mg/dL have a day-to-day reproducibility of 1.8% (SD=1.6) and 1.7% (SD=3.5), respectively. The concentration of High Density Lipoprotein Cholesterol will be determined using a direct enzymatic colorimetric assay.¹⁵⁹ HDL-C at the concentrations of 27.0 and 54.9 mg/dL have a day-to-day reproducibility of 3.3 (SD=0.9) and 1.7% (SD=0.9), respectively. Low Density Lipoprotein Cholesterol will be determined by a homogenous direct method;¹⁶⁰ day-to-day variabilities at concentrations of 90, 106, and 129 mg/dL are 3.01, 2.34 and 2.18%, respectively. The concentration of High Sensitivity CReactive Protein (hsCRP) will be determined using an immunoturbidimetric assay on the Roche P Modular system using reagents and calibrators from DiaSorin (Stillwater, MN); day-to-day variabilities of the assay at concentrations of 0.91, 3.07 and 13.38 mg/L are 2.81, 1.61 and 1.1%, respectively.

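### Table 3's two HbA1c rows imply a mean HbA1c of about 3.5, so they cannot both be projections for the same women; the CRP row also needs its unit confirmed and its figure corrected

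*Combined protocol and SAP*

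**What the plan says.** Section D.17 gives, for each outcome, the difference between arms "which we could detect at 80% power using standard deviations based on our prior studies and the literature", "using 2-sided tests with a significance level of alpha=5% (NCSS PASS 2008 software"). The design "requires 300 participants (150 in each intervention arm) at the time of delivery".

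Table 3 has two adjacent HbA1c rows under one SD column, both with 300 women:

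- absolute change: SD 0.26, detectable difference 0.1, no unit printed;
- percent change: SD 7.4%, detectable difference 2.4%.

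The text takes the percent row as its example ("we have 80% power to detect as small as a 2.4% difference (Table 3) in percent change in HbA1c between treatment arms") and sets it against an outside result: "A comparable trial among Hispanics observed a 7.1% difference in percent change in HbA1c between treatment arms". No baseline mean HbA1c is given, and no source is tied to either row. The only HbA1c levels in the document are in the assay description in D.12.1: "The day-to-day variability at values of 5.5 and 9.1 are 1.9 and 3.0%, respectively".

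The CRP row of Table 3 is in mg/dl, with N=264, SD 4.50 and detectable difference 1.5. D.12.1 describes the hsCRP assay at "concentrations of 0.91, 3.07 and 13.38 mg/L".

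**The concern.** An SD of absolute change and an SD of percent change for the same measurement in the same women are linked through the mean. Once the mean is fixed, one determines the other. The two HbA1c rows imply a mean well below the lower of the two assay levels that the plan quotes, so at least one SD does not describe the women to be enrolled.

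This matters because HbA1c is the only Table 3 outcome for which the plan argues, from an observed trial effect, that its detectable difference is achievable. If the larger SD is right, the absolute row promises more sensitivity than the trial has. If the smaller is right, the worked example does not give the smallest detectable difference. Rounding the absolute row to one decimal hides the conflict.

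The CRP row raises a smaller question of the same kind: its unit differs from the assay section's, and its detectable difference does not follow from its own SD and N.

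**Working it through.** **Inputs from D.17 and Table 3.** Two-sided alpha 5%, power 80%, 150 per arm for HbA1c, 132 per arm (264/2) for CRP; SDs 0.26, 7.4% and 4.50.

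**Reproducing the plan's figures.** Detectable difference = SD × (1.960 + 0.842) × √(2/n).

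- n=150: the multiplier is 2.802 × √(2/150) = 0.3235, or 0.3245 with the t distribution.
- Percent row: 7.4 × 0.3245 = 2.40%. Printed 2.4%; it reproduces.
- Absolute row: 0.26 × 0.3245 = 0.084. Printed 0.1, which is consistent with rounding to one decimal.
- Other readings do not give 2.4%: a one-sided test gives 2.12%, removing 20% of the variance for covariates gives 2.14%, and 132 per arm gives 2.56%.

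**Linking the rows.** SD(percent change) ≈ SD(change)/mean. The implied mean is 0.26/0.074 = 3.51. Allowing for rounding of both SDs, it lies between 0.255/0.0745 = 3.42 and 0.265/0.0735 = 3.61.

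**Could baseline spread explain the gap?** A simulation held the SD of change at 0.26, with baseline mean 5.3 or 5.5, baseline SD 0.3 to 0.8 and mean change 0 to −0.5. The percent-change SD came out at 4.75 to 5.34%, well short of 7.4%.

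**What changes under each SD.** The document gives no baseline mean. A range of 4.8 to 5.8 is assumed, in percentage points, with 5.5 shown as the middle case.

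| Assumed mean | Absolute SD if 7.4% is right (0.074 × mean) | Detectable absolute difference | Power at 0.1 | Percent SD if 0.26 is right (26/mean) | Detectable percent difference |
|---|---|---|---|---|---|
| 4.8 | 0.36 | 0.12 | 68% | 5.4% | 1.8% |
| 5.5 | 0.41 | 0.13 | 56% | 4.7% | 1.5% |
| 5.8 | 0.43 | 0.14 | 52% | 4.5% | 1.5% |

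At the unrounded 0.084, power in the 7.4% case is 40 to 54%. The two SDs disagree by a factor of 7.4/5.4 = 1.37 to 7.4/4.5 = 1.65.

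**Against the cited 7.1% effect.** 7.1/7.4 = 0.96 SD with the larger SD. With the smaller it is 7.1/5.4 = 1.3 to 7.1/4.5 = 1.6 SD. The trial can detect about 0.32 SD, so power exceeds 99.9% in every case.

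**CRP.** For n=132 the multiplier is 0.346, and 4.50 × 0.346 = 1.56, which rounds to 1.6 rather than 1.5. Read literally, 1.5 mg/dl is 15 mg/L, above the highest level (13.38 mg/L) at which assay precision is quoted.

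**The case against.** The strongest reply is that the plan never says the two SDs come from one source. D.17 cites several studies without assigning them to rows, so each SD could be true where it was observed. No baseline mean is stated, and 5.5 is a level at which assay precision was quoted, not a trial mean. This stands as an account of how the rows may have arisen. It does not reconcile them: Table 3 projects what one cohort of 300 women will show, and that cohort cannot have both SDs at any mean in the assumed range.

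A reader might infer that the 2.4% example is wrong. The document does not support that. The figure follows from its own inputs; it is correct if 7.4% holds and conservative if 0.26 holds. A reader might also infer that the trial is underpowered for HbA1c. That is not supported either, since power against the cited effect is ample under both SDs. The 52 to 68% is power at a rounded table entry rather than at a stated design target, and a corrected 0.12 to 0.14 would still print as 0.1 at the table's precision.

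On CRP, a tenfold unit error is tempting but not proved. The quoted concentrations are precision levels, not the assay's range or the population's spread, and Table 3 also gives insulin in a different unit from the assay section. What stands is a unit to confirm and an arithmetic slip.

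**Conclusion.** The HbA1c rows are incompatible as projections for the same women, so at least one SD and its detectable difference must change. This rests on both rows describing the enrolled cohort, on the 0.26 being in HbA1c percentage points, and on a mean near 4.8 to 5.8.

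Only the absolute row can be optimistic, by a factor of about 1.4 to 1.65. The percent example is either right or cautious. The sample size, the analysis and the argument from the 7.1% effect are unaffected; HbA1c is one of several Aim 2 biomarkers. The point is worth correcting because an 80% power statement rests on inputs that disagree, and the correction is cheap.

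For CRP, the printed 1.5 should be 1.6 on the stated SD and N. The intended unit is open.

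**What to change.** - Choose one source for the SD of HbA1c change, in women like those to be enrolled. State the source, its baseline mean and the unit.
- Derive both HbA1c rows from it, and print the absolute detectable difference to at least two decimals.
- Update the 2.4% example in the text if the percent SD changes. The comparison with 7.1% can stay.
- Confirm whether the CRP row is in mg/dl or mg/L. Restate the row if the unit changes; if SD 4.50 is kept, print 1.6.

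The cost is three table rows and possibly a sentence of text, with no change to design, sample size or analysis. The absolute HbA1c figure may become less favourable.

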Based on observed rates in our 2 trials (R01DK074876 and ASPH/CDC S3948), we conservatively expect to 333 women over the 24 mos recruitment period. We expect 10% of women to leave the New England area, deliver elsewhere, or withdraw during pregnancy, and therefore expect 300 participants (150 in each intervention arm) at the time of delivery. We calculate that 4% of women will be excluded for very early preterm birth (<34 wks), miscarriage, or stillbirth resulting in 288 children at delivery. Over the following 1 yr, we conservatively project that an additional 8% of women will be lost to follow-up due to withdrawal or movement out of the New England area. Women who become pregnant again will be censored. Therefore, we expect 264 women and children at 1 yr postpartum.

[figure not shown]
Bilingual (Spanish and English) and bicultural health educators will recruit women at the first prenatal care visit (~10 wks gestation). Women will be informed of the aims/procedures of the project, sign an informed consent, and complete a screening form to determine eligibility.

The recruitment sites will include the Wesson Women's Clinic, Baystate Midwifery and Women's Health, Baystate Maternal-Fetal Medicine and the Baystate Perinatal Diagnostic Center. Screening is done prior to the patient's visit by a research assistant. A Centricity appointment report is reviewed which provides all women with OB appointments in the above locations. This report has the patients' name, medical record number, date of birth, ethnicity, last menstrual period, appointment reason, appointment time and location.

Based on information from the Baystate nutritionist and the Centricity roster, the research assistants will develop a potential participant list. This list will be maintained as a project on the UMASSMED REDCap server. This project will only be accessible to Baystate IRB approved staff. The pre-screened patients are then approached to determine if they are interested in participating in the study. If they are not eligible, the research assistant enters their status and/or reason for ineligibility. If women are eligible and interested, they will be informed of the aims and procedures of the project, sign an informed consent and HIPAA release, and the research assistant will initiate study procedures. If this cannot be completed in person, it will be completed over the telephone.

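### The stated 80% power for a 30% reduction in exceeding the IOM guidelines is about 77% at the plan's 150 women per arm; 80% power corresponds to about a 31% reduction

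*Combined protocol and SAP*

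**What the plan says.** Section D.17 claims "we have 80% power to detect a 30% reduction in risk or larger for exceeding IOM guidelines", "given our observation that 51% of overweight/obese Hispanic women exceeded guidelines in the study population". The test settings given earlier in the same paragraph are "using 2-sided tests with a significance level of alpha=5" per cent. No sample size or test is attached to the binary claim itself.

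The sample size for the power section as a whole is given at its start: it "requires 300 participants (150 in each intervention arm) at the time of delivery". Because 10% are expected to be lost before delivery, the team "therefore will recruit 333 women over the 24 mos recruitment period". Table 3 uses N=300 for GWG, the continuous form of the same outcome.

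The plan describes the 4% exclusion in two ways:

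- D.17 ties it to the children: "For offspring outcomes, we calculate that 4% will be excluded for very early preterm birth (<34 wks), miscarriage, or stillbirth".
- D3 ties it to the mothers: "We calculate that 4% of women will be excluded for very early preterm birth (<34 wks), miscarriage, or stillbirth". D2 and section E (Human Subjects Involvement and Characteristics) agree with D3: "Women who have a very early preterm birth (<34 wks), a miscarriage, or a still birth after enrollment or a stillbirth will be excluded".

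**The concern.** A power statement should follow from its stated inputs. Here the control rate, effect, level and sidedness are given, and the surrounding text supplies the sample size, but together they do not give 80%. The sentence sets a floor (30% or larger), so a true 30% reduction ought to carry at least 80% power, and it does not.

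Reducing excess GWG is a central goal of the trial, and this is the only power statement for a binary outcome. A reader would take the design to be slightly more sensitive than it is. The open question about the 4% exclusion means that the denominator for this outcome cannot be read from the plan either.

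**Working it through.** **Inputs.** Control rate 51% (D.17). A 30% relative reduction gives 0.51 × 0.70 = 0.357. Two-sided 5% (D.17). 150 per arm (D.17), with equal allocation (D.5).

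**The plan's figure on the plan's inputs.** For the pooled two-proportion z test,

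power = Φ[(p₁ − p₂ − 1.96·SE₀) / SE₁], with SE₀ = √(2·p̄(1 − p̄)/n) and SE₁ = √((p₁(1 − p₁) + p₂(1 − p₂))/n).

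- p̄ = (0.51 + 0.357)/2 = 0.4335
- SE₀ = √(2 × 0.4335 × 0.5665/150) = 0.0572
- SE₁ = √((0.2499 + 0.2296)/150) = 0.0565
- power = Φ[(0.153 − 1.96 × 0.05722)/0.05654] = Φ(0.722) = 76.5%

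The stated 80% is not reproduced.

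**Other tests and the smaller denominator** (300 × 0.96 = 288, or 144 per arm):

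| Test | 51% v 35.7%, n=150 | 51% v 35%, n=150 | Reduction detectable at 80%, n=150 | 51% v 35.7%, n=144 | 51% v 35%, n=144 | Reduction detectable at 80%, n=144 |
|---|---|---|---|---|---|---|
| Pooled z | 76.5% | 80.2% | 31.3% | 74.8% | 78.6% | 31.9% |
| Arcsine | 76.6% | 80.3% | 31.3% | 74.9% | 78.7% | 31.9% |
| Unpooled z | 77.2% | 81.0% | 31.0% | 75.5% | 79.4% | 31.6% |
| Pooled z, exact enumeration | 77.7% | 81.2% | 30.9% | 74.8% | 78.6% | 31.9% |

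Other methods at 150 per arm are lower: log odds ratio 75.9%, log relative risk 74.8%, Fisher's exact 74.0%, continuity-corrected 72.7%. With the pooled test, 80% power for a 30% reduction needs 164 per arm.

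**Where the 30% might come from.**

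- *Rounding.* 51% against a whole-percent 35% reaches 80%, but that reduction is 1 − 35/51 = 31.4%.
- *All 333 recruited.* At 166 or 167 per arm, a 30% reduction has 80.6% to 81.6% power. But 333 is the number before the 10% loss (333 × 0.90 ≈ 300), and no row of Table 3 or 4 uses it.
- *Covariates explaining 20% of variation.* D.17 limits this to multiple regression models. Applied here it gives an effective 150/0.8 = 187.5 per arm and about 85%, not 80%.
- *One-sided test.* This gives about 85% and contradicts the stated two-sided tests.
- *30% read as an odds ratio of 0.70.* This gives about 34%.

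The documents do not show which, if any, was used.

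**The denominator.** D.17 reaches 264 women at one year by 300 × 0.96 × 0.92 = 264.96. The maternal one-year rows of Table 3 therefore already carry the 4% exclusion, although D.17 introduces it for offspring outcomes, while GWG at delivery stays at 300.

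**Check on Tables 3 and 4.** An unadjusted two-sample t test at the printed N and SD (80% power, two-sided 5%) reproduces 33 of the 35 rows to the printed digit, including GWG (2.27, printed 2.3; 2.32 if N=288). Two rows of Table 3 do not match:

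- Total caloric intake, SD 64.90: 21.1 at the printed N=300, but 22.4 is printed. At N=264 the value is 22.46, so either the N or the value is off.
- CRP, SD 4.50: 1.558 at the printed N=264, which rounds to 1.6, but 1.5 is printed. At N=300 the value would be 1.46.

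**The case against.** The strongest reply is that the gap is too small to matter. The target rate moves from 35.7% to 35.05%, and 0.0065 × 150 is about one woman per arm. A control rate of 53.5% in place of 51% would give 80% power for exactly a 30% reduction, and the 51% is a prior observation quoted without any measure of precision. The same paragraph also rounds loosely: 0.325 to 0.346 SD is described as roughly 0.30 to 0.35. On this view the 30% is a casually rounded 31%. In addition, the caloric-intake cell errs on the cautious side, the CRP cell is a last-digit slip, and the 4% exclusion is really a question about the analysis population, which bears on the intention-to-treat statement in D.16.

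Much of this stands. The consequence is small and the origin of the 30% is unknown. The table cells and the exclusion wording add no weight to the power discrepancy itself. What does not stand is the figure: 31.3% rounds to 31%, the sentence carries no approximation sign, and no two-sided unadjusted method tried at 150 per arm comes within 2 points of 80%. Uncertainty in the 51% affects how much trust to place in any power figure, but it does not make this one follow from its inputs: control rates of 50.5% to 51.5% give only 75.8% to 77.2% (pooled).

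**Conclusion.** The sentence is wrong as written, and the error is minor. With 300 women at delivery, a 30% reduction from 51% has 76.5% to 77.7% power, which is 2.3 to 3.5 points below the stated 80%. The reduction detectable at 80% power is 30.9% to 31.3% (51% to between 35.0% and 35.3%). If the 4% exclusion applies to maternal outcomes, power is 74.8% to 75.5% and the detectable reduction is 31.6% to 31.9%.

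These ranges cover the pooled, arcsine, unpooled and exact-enumeration z tests. They assume 1:1 allocation, a two-sided 5% level, a control rate of exactly 51% and no covariate adjustment. Confidence is high in the recomputation, not in any explanation of how the 30% arose. The primary mixed-model analysis, the GWG row and the planned sample size are unaffected.

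**What to change.** - Restate the binary claim in D.17 as 80% power to detect about a 31% reduction (51% to about 35%) with 300 women at delivery, and name the test.
- Reconcile D2, D3 and section E with D.17 and Table 3 on whether women with birth before 34 weeks, miscarriage or stillbirth are left out of maternal outcomes. If they are, use N=288 and state about 32%; the GWG row still prints as 2.3.
- In Table 3, make the N and the value in the caloric-intake row agree (21.1 at N=300; 22.5 at N=264), and print CRP as 1.6 at N=264.

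The cost is one restated sentence, one reconciled statement and two table cells. It needs no extra participants and no change to the design or analysis.
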